4.5. Prior and Concomitant Medications

Prior and Concomitant medications will be coded using the World Health Organization Drug Dictionary (WHO-DD). Concomitant medications are defined as any therapy used on or after the same day as the first dose of study agent, including those that continue on after the first dose of study agent.

Summaries of concomitant medications will be presented by therapeutic class, pharmacologic class, drug name and treatment group. The proportion of subjects who receive each concomitant medication will be summarized as well as the proportion of subjects who receive at least 1 concomitant medication.

Prior therapies used for induction will be summarized by the drugs captured on the CRF pages.

4.6. Subsequent Antimyeloma Therapy

The total number of subjects who received subsequent antimyeloma therapy will be reported for safety analysis set in each treatment group. A summary of all subsequent antimyeloma therapies as well as the first line of subsequent therapies will be presented by therapeutic class, pharmacologic class and drug name, coded using the WHO Drug Dictionary.

In addition, for subjects who received subsequent antimyeloma therapy, their best response based on investigator's assessments to the first subsequent antimyeloma therapy will be summarized.

5. EFFICACY

5.1. Analysis Specifications

5.1.1. Level of Significance

All statistical hypothesis tests and 95% confidence intervals presented will be 2-sided.

The primary hypothesis is to be tested at the 0.05 significance level (overall).

If the primary endpoint of the MRD negativity (10^{-5}) conversion rate from baseline to 12 months after initiation of maintenance treatment is statistically significant, the key secondary endpoint PFS will be sequentially tested with an overall two-sided alpha of 0.05, by utilizing a hierarchical testing approach as proposed by Tang and Geller (1999)³ that strongly controls Type I error rate.

One interim analysis on the key secondary endpoint, PFS, using the Obrien-Fleming alpha spending function is planned at the time of primary endpoint analysis.

Analyses on all other efficacy endpoints are exploratory and will be tested at 2-sided 0.05 significant level without multiplicity adjustment.

5.1.2. Data Handling Rules

Data handling rules for the primary efficacy endpoint is given in section 5.2.1. There is no imputation planned for the other missing efficacy endpoint values.

5.2. Primary Efficacy Endpoint(s)

The MRD conversion rate from baseline to 12 months after maintenance treatment (defined as the proportion of patients who have achieved MRD negative status [at 10⁻⁵] by 12 months after the start of maintenance treatment) as determined by NGS.

5.2.1. Definition

The primary endpoint of this study is the MRD conversion rate from baseline to 12 months after start of maintenance treatment. It is defined as the proportion of subjects who were MRD [at 10⁻⁵] positive at baseline and have achieved MRD negative status [at 10⁻⁵] as determined by NGS by 12 months of maintenance treatment. The primary endpoint will be analyzed based on FAS.

Subjects' MRD positive status at baseline should be verified. Since subjects do not always adhere to the protocol visit schedule, the post-baseline MRD records from randomization up to 12-month + 2 months will be selected for MRD negativity status evaluation. Subjects with missing or unevaluable MRD status will be considered as MRD positive. Subjects who have achieved MRD negative status on or after PD or switch to subsequent anti-myeloma therapy before PD, will not be considered MRD negative in the primary endpoint analysis.

5.2.2. Estimand

The primary estimand, the main clinical quantity of interest to be estimated in the study, is defined by the following 5 components:

- Population: subjects with newly diagnosed multiple m yeloma eligible for transplant who are \geq VGPR post ASCT and MRD [at 10⁻⁵] positive
- Treatment: subjects randomized at 1:1 to DR or R for 36 cycles maintenance treatment
- Variable: a binary variable for the MRD conversion rate from baseline to 12 months after maintenance treatment (defined as the proportion of patients who have achieved MRD negative status [at 10⁻⁵] by 12 months after start of maintenance treatment prior to the intercurrent events of subsequent antimyeloma therapy or PD) as determined by NGS.
- Intercurrent event (ICE):
 - subsequent antimyeloma therapy
 - o PD
 - composite strategy will be used to count for the intercurrent events as reflected in the variable definition
- Population-level summary: odds ratio of MRD conversion rate for DR vs. R treatment groups

5.2.3. Analysis Methods

The MRD conversion rate will be calculated for each treatment group based on the FAS. The corresponding 95% exact CI will be provided.

The stratified Cochran-Mantel-Haenszel (CMH) method will be used to test if the MRD conversion rate is the same between the two treatment groups. Stratification factor included in the analysis is baseline cytogenetic risk per investigator's assessment (high risk versus standard/unknown risk) as used for randomization of the study. The estimate of odds ratio and its 95% confidence interval will be provided. P-value will be provided by Fisher's exact test.

The following supplemental analyses may be performed in a similar manner as described above:

- MRD negativity conversion rate (10-5) by 12-months for the MRD-evaluable analysis set
- MRD negativity conversion rate (10-5) by 12-months for subjects in FAS who achieved CR or better response per computerized algorithm at any time during the study
- MRD negative (10⁻⁵) CR conversion rate by 12 months of maintenance treatment in FAS where MRD negative CR conversion rate is defined as the proportion of subjects achieved MRD negativity and CR or better response by 12-months of maintenance treatment according to IMWG criteria per computer algorithm
- MRD negativity rate at 10⁻⁴, 10⁻⁵ and 10⁻⁶ by 12 months of maintenance treatment in FAS
- MRD negativity (10⁻⁵) conversion rate by 12-months of maintenance treatment by subgroups of subjects according to Section 2.4. Analysis will be performed similarly as

the primary analysis except that randomization stratification factor will be excluded from CMH test. Forest plot will be generated.

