MRD (aspirate) by NGS	X (NGS)	At the end of 12, 18, 24, and 36 months (NGS), (ie, C13D1, C19D1, C25D1 and at the EOT visit)	X		 During Screening: NGS assay (Adaptive Biotechnologies' NGS-based MRD assay) to be done on bone marrow aspirate collected during screening to determine eligibility for study entry. Residual samples, if available, will also be banked for future tests. Two sequential NGS assays will be done during screening. The first NGS assay will be conducted on archived bone marrow samples for calibration and identification of the index myeloma clone. Obtain archived bone marrow samples as described in Inclusion Criterion #4. If an existing result on index myeloma clone is available from Adaptive Biotechnologies' NGS-based MRD assay, conducted as part of institutional procedures, then archived bone marrow sample is not required as long as Adaptive Biotechnologies is able to retrieve historical results on the index myeloma clone from the clinical database. Following index clone calibration (or verification of existing index clone results from a previously conducted Adaptive Biotechnologies' NGS-based MRD assay), MRD will be assessed by NGS (Adaptive Biotechnologies' NGS-based MRD assay), using fresh bone marrow aspirate sample collected during screening. Note: If Adaptive Biotechnologies ' NGS- based MRD assay was conducted post-ASCT as part of institutional procedures and MRD results are available at screening, these results are to be recorded in the eCRF. Patients who are MRD positive at 10⁻⁵ based on an existing post-ASCT NGS assay conducted by Adaptive Biotechnologies, are eligible to participate. Such patients will not be required to undergo NGS based MRD assessment again during screening. After the start of study treatment (after C1D1):
-----------------------	---------	--	---	--	---

		STUDY PHA			
PROCEDURE	SCREENING	Maintenance (Cycles 1–36)	ЕОТ	Follow-up (from the date of last study treatment until the end of study)	Notes
					 NGS is to be conducted at 12, 18, 24, and 36 months: During the bone marrow aspirate procedure, the first aspirate sample that is drawn will be sent to the central laboratory to determine MRD by NGS. All bone marrow aspirates to be sent to the central laboratory should be at least 3 mL. Additional bone marrow aspirate samples may be taken and used for local laboratory testing. Bone marrow aspirate collected within ±30 days of the scheduled visit during the maintenance phase is acceptable.

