11.3.1. Primary Endpoint and Analysis

The primary endpoint is the MRD conversion rate from baseline to 12 months after maintenance treatment as determined by NGS, which is the proportion of patients who have achieved MRD negative status [at 10⁻⁵] by 12 months after maintenance treatment prior to progressive disease (PD) or subsequent anti-myeloma therapy. Patients who have achieved MRD negative status on or after PD or switch to subsequent anti-myeloma therapy before PD, will not be considered MRD negative in the primary endpoint analysis.

The MRD conversion rate will be compared between the 2 treatment groups based on the intentto-treat population using the stratified Cochran Mantel-Haenszel test with baseline cytogenetic risk (high versus standard/unknown) as stratification factor. A Mantel-Haenszel odds ratio along with its 2-sided 95% CIs will be calculated.

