1.4. Sample Size Justification

Based on previous reports of MRD negativity rate in lenalidomide-treated myeloma patients, the anticipated MRD (at 10⁻⁵) negativity conversion rate is estimated to be 20% for patients treated with lenalidomide alone following post ASCT. Assuming a 20% absolute increase in MRD negativity rate (40% daratumumab plus lenalidomide versus 20% lenalidomide alone) by the end of 12-month maintenance treatment, a sample size of 214 patients (ie, 107 patients per treatment group at 1:1 randomization) will be needed to achieve at least 85% of power to detect such a treatment difference at a 2-sided alpha of 0.05 using continuity corrected chi-squared test.

Disease assessments for each patient will continue until 36 months from the date of randomization of the last patient. It is anticipated that this will yield 64 PFS events and provide approximately 79% power to detect a 50% reduction in the risk of progression or death (HR=0.50, translating to an improvement in median PFS from 60 months to 120 months) with a log-rank test at a 2-sided alpha of 0.05 with an accrual period of 1 year. One interim analysis using Obrien-Fleming alpha spending function is planned at the time of primary endpoint analysis when approximately 32 events are anticipated.

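### The primary test of MRD conversion is valid and reaches its stated power, but by ignoring baseline MRD level it forgoes efficiency and leaves chance imbalance in that level uncorrected

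*SAP*

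**What the plan says.** **Primary test.** SAP 5.2.3: "The stratified Cochran-Mantel-Haenszel (CMH) method will be used to test if the MRD conversion rate is the same between the two treatment groups". The section names one factor only, split into high versus standard/unknown: "Stratification factor included in the analysis is baseline cytogenetic risk". Protocol 11.3.1 has the same single factor, with the comparison made "using the stratified Cochran Mantel-Haenszel test with baseline cytogenetic risk". SAP 5.2.3 then takes the p-value from Fisher's exact test, which has no strata.

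**Use of baseline MRD.** SAP 5.2.1 uses baseline MRD only as a status: positive at 10⁻⁵, to be verified. The level is not a randomization stratum (Protocol 5, SAP 1.5), a subgroup (SAP Table 1), a baseline characteristic (SAP Table 3) or part of any supplemental analysis in SAP 5.2.3.

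**Source of the level.** Protocol 3.2.5, 4.1 and 9.3.4 use one vendor's sequencing assay for both entry and follow-up. For patients already tested after transplant, the Time and Events Schedule Part 1 says that where "MRD results are available at screening, these results are to be recorded in the eCRF". Those positive at 10⁻⁵ on such a test need no repeat.

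**Sample size.** SAP 1.4 assumes "40% daratumumab plus lenalidomide versus 20% lenalidomide alone" with 107 patients per arm, which "will be needed to achieve at least 85% of power". The planning calculation is set "at a 2-sided alpha of 0.05 using continuity corrected chi-squared test".

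**The concern.** The endpoint is a fall below a fixed threshold on an assay that has already been run at entry. A patient who enters at 2×10⁻⁵ needs a two-fold fall; one who enters at 10⁻² needs a 1000-fold fall. Some link between baseline level and conversion is therefore built into the endpoint, whereas the plan states no such link for cytogenetic risk, the one factor it uses.

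Two things are at stake. A stratified test that used the level could have more power at the same sample size. And if one arm happened to enter with lower MRD, the odds ratio would move in its favour, with no planned table to show this and no planned analysis to allow for it.

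**Working it through.** **1. The plan's own figure.** Inputs from SAP 1.4: p₁ = 0.20, p₂ = 0.40, mean 0.30, difference 0.20, two-sided alpha 0.05. For 85% power (z = 1.036):

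- Uncorrected n per arm = [1.96√(2×0.3×0.7) + 1.036√(0.16+0.24)]² / 0.20² = (1.270 + 0.655)² / 0.04 ≈ 92.7
- Continuity-corrected n = (92.7/4)·[1 + √(1 + 4/(92.7×0.2))]² ≈ 102.5, so 103 per arm

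Solving the same formula for power at 107 per arm gives 86.6%. Exact enumeration gives 86.7% (corrected chi-squared), 87.1% (Fisher) and 89.9% (uncorrected chi-squared). The claim of at least 85% holds with no baseline MRD term.

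**2. Power with baseline MRD bands.** The documents give neither the distribution of baseline MRD nor its prognostic strength, so both are assumptions here. All runs use 107 per arm, marginal rates of 20% and 40%, and 20% high cytogenetic risk.

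*Logistic model.* Baseline log₁₀ MRD is uniform from −5 to −2, with bands below 10⁻⁴, 10⁻⁴ to 10⁻³, and above 10⁻³; 3000 trials per row.

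| Fall in odds per log₁₀ | CMH, cytogenetic risk only | CMH, plus 3 MRD bands | Change (points) |
|---|---|---|---|
| none | 89.2% | 88.3% | −0.9 |
| 2-fold | 89.5% | 91.3% | +1.8 |
| 3-fold | 90.0% | 92.6% | +2.6 |
| 5-fold | 90.5% | 96.1% | +5.6 |
| 10-fold | 89.8% | 97.4% | +7.6 |

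The Monte Carlo standard error of one entry near 90% is √(0.9×0.1/3000) ≈ 0.5 points. A uniform variable over 3 logs has SD 3/√12 = 0.87, so 3-, 5- and 10-fold per log₁₀ are odds ratios of about 2.6, 4.0 and 7.3 per SD. Type I error of the banded test was 4.4% to 5.6%.

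*Normal baseline log MRD, tertiles added.* For odds ratios of 1, 1.5, 2, 3 and 4 per SD, the planned test has power 89.6, 89.8, 90.0, 89.1 and 88.8%. With tertiles it has 88.6, 89.8, 91.7, 92.4 and 93.9%.

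*Threshold model.* Baseline lies 0 to 3 logs above 10⁻⁵, and a patient converts if the log reduction exceeds that distance; 5000 trials per row.

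| SD of log reduction | Missing, counted as not converted | Planned CMH | Plus 3 bands |
|---|---|---|---|
| 1 | 0 | 89.5% | 96.2% |
| 1 | 15% | 89.4% | 94.8% |
| 2 | 0 | 90.1% | 92.3% |
| 2 | 15% | 89.9% | 91.5% |
| 3 | 0 | 89.4% | 89.6% |
| 3 | 15% | 90.2% | 90.4% |

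Across all models the change runs from about −1 to +8 points.

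**3. Chance imbalance.** The standard error of the between-arm difference in mean baseline log MRD is √(2/107) = 0.137 SD. Take no treatment effect and 20% conversion, move the two arms' baseline distributions apart by 1 or 2 standard errors, and average the logistic probability over each.

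| Odds ratio per SD | 1 SE: rate difference (odds ratio) | 2 SE: rate difference (odds ratio) |
|---|---|---|
| 1.5 | 0.9 points (1.06) | 1.7 points (1.11) |
| 2 | 1.4 points (1.09) | 2.8 points (1.19) |
| 3 | 2.0 points (1.14) | 4.1 points (1.29) |
| 4 | 2.4 points (1.16) | 4.7 points (1.34) |

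In the threshold model, overall two-sided type I error of the planned CMH was 4.5% to 5.5%. Among simulated trials with an imbalance above 1 SE favouring the daratumumab arm, its one-sided error was 4.5% to 7.7% against a nominal 2.5%. With bands it was 1.9% to 3.2%.

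**The case against.** Analysing by the randomization factor is a valid primary analysis, and covariate adjustment is optional. That stands. A reader might infer that the trial loses power against its plan, or is underpowered. Step 1 shows otherwise.

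The gain depends on an unstated prognostic strength. With an odds ratio of 1.5 per SD, tertiles gain nothing, and the weakest threshold model gains 0.2 points. That stands too, which is why only a range is given.

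Availability of the level is not shown. The readings at 10⁻⁴, 10⁻⁵ and 10⁻⁶ in SAP 5.2.3 concern negativity by 12 months. No section says that a quantitative baseline level is kept for analysis. SAP 2.3.1 defines a subset who have a baseline assessment, and some baseline results are earlier institutional tests. The level must be confirmed as retrievable before anything is built on it.

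Adding a stratum may also not reach the reported result. While SAP 5.2.3 takes the p-value from Fisher's test, no stratum affects it. This is correct, and the fix has to deal with it.

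Finally, the trial is open-label (Protocol 5), the sponsor runs the primary analysis (Protocol 11.7), and the SAP is already at version 2.0. New strata chosen late invite doubt. That limits when the primary test may change, but it does not argue against a sensitivity analysis or a baseline table.

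**Conclusion.** The point holds as a worthwhile improvement, not as an error. The omission of baseline MRD level is plain in both documents. Its cost is forgone efficiency of up to about 8 points of power, with a risk of about 1 point the other way if the level is not prognostic. A 2-SE imbalance could shift the rate difference by about 3 to 5 points if the odds ratio is 2 to 4 per SD. All these sizes rest on the assumed distributions and strengths above.

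Three stronger readings are not supported:

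- **Inflated type I error.** Overall error stays near 5%. Only error conditional on an imbalance rises.
- **A large imbalance in the covariate as an equally large bias.** If a third of patients enter below 10⁻⁴, the between-arm difference in that share has SD √(2×0.33×0.67/107) = 6.4 points, or about ±13 points as a 95% range. That describes the covariate. The shift in the result is the much smaller figure in step 3.
- **A fixed saving in sample size.** At 5-fold odds, [(1.96+1.76)/(1.96+1.31)]² = 1.29, but that slope is one assumed value among several.

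**What to change.** 1. Confirm that the quantitative baseline level, from screening or from an accepted institutional test, can be retrieved for each patient.
2. Prespecify in SAP 5.2.3 a CMH test stratified by cytogenetic risk and baseline MRD band, for example 10⁻⁵ to <10⁻⁴, 10⁻⁴ to <10⁻³, and ≥10⁻³.
3. Add a rule for patients with no retrievable level and for those below 10⁻⁵. The latter can exist because the screening route in Protocol 4.1 asks only for detectable MRD, and Protocol 3.2.5 describes an assay that detects one cell in a million. On the wording of SAP 5.2.1 such patients cannot convert, so a separate band for them would add nothing to the CMH statistic; the SAP should say where they are counted.
4. Make this the primary test, with a matching amendment to Protocol 11.3.1, only if no 12-month data have been seen by arm. The documents do not settle whether that is so. Otherwise make it a dated, prespecified sensitivity analysis.
5. Take the p-value from the stratified CMH test instead of Fisher's test.
6. State in SAP 5.2.2 whether the odds ratio is conditional or marginal. The marginal value at planning is (0.4/0.6)/(0.2/0.8) = 2.67; conditional values in the simulated range were 2.75 to 3.66.
7. Add baseline MRD band to SAP Tables 1 and 3.

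Cost: SAP wording, plus a short protocol amendment if the primary test changes. The downsides are up to about 1 point of power if the level is not prognostic, and an odds ratio that is conditional on baseline MRD. With 20% high risk assumed, the smallest strata hold about 214×0.2/3 ≈ 14 patients; the simulated type I error shows that this is workable.

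### The SAP tests the primary endpoint with stratified CMH but takes the p-value from Fisher's exact test, so the decision rule that also gates PFS is not unique

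*SAP*

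**What the plan says.** Protocol 11.3.1 compares the MRD conversion rate in the intent-to-treat population "using the stratified Cochran Mantel-Haenszel test with baseline cytogenetic risk (high versus standard/unknown) as stratification factor", with a Mantel-Haenszel odds ratio and 95% CI. The protocol synopsis says the same. Neither mentions Fisher's exact test.

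SAP 5.2.3 begins in agreement: "The stratified Cochran-Mantel-Haenszel (CMH) method will be used to test if the MRD conversion rate is the same between the two treatment groups". The stratification factor is cytogenetic risk as used for randomisation, and an odds ratio with a 95% CI is to be given. The paragraph then ends: "P-value will be provided by Fisher's exact test". That is the only p-value the section mentions. It is not called supportive, it is not limited to sparse tables, and no stratified exact version is described.

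Under SAP 5.1.1, if the primary endpoint is significant, "the key secondary endpoint PFS will be sequentially tested with an overall two-sided alpha of 0.05". SAP 5.4.2 carries the 5.2.3 method over to overall MRD conversion, durable MRD negativity, CR or better, and sCR.

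**The concern.** There is one confirmatory comparison, and the SAP gives it two tests. Stratified CMH conditions on cytogenetic risk. Fisher's exact test in its standard form works on the single pooled 2x2 table, ignores the stratum, and is conservative at this sample size. Read literally, the SAP would print a stratified odds ratio and CI beside a p-value from a different test, and the two could disagree about the null.

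Two things are at stake: whether the trial meets its primary endpoint, and whether PFS may be tested at all. The study is open-label and the sponsor conducts the primary analysis, so the source of the deciding p-value should be fixed before the data are analysed.

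**Working it through.** **Inputs.** From SAP 1.4: 107 patients per arm, 1:1, "40% daratumumab plus lenalidomide versus 20% lenalidomide alone", power of at least 85%, two-sided alpha 0.05, continuity-corrected chi-squared test for planning. From SAP 5.2.3: two strata. The documents do not give the high-risk share, so 15%, 20% and 30% were assumed.

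**The plan's own figure.** With p1 = 0.40, p0 = 0.20, pooled p = 0.30 and n = 107:

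- SE under the null = sqrt(2 × 0.30 × 0.70 / 107) = 0.0627
- SE under the alternative = sqrt((0.40 × 0.60 + 0.20 × 0.80) / 107) = 0.0611
- Power with continuity correction = Φ[(0.20 − 1/107 − 1.96 × 0.0627) / 0.0611] = 86.6%
- Power without correction = Φ[(0.20 − 1.96 × 0.0627) / 0.0611] = 89.7%

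The stated power of at least 85% is reproduced; 103 per arm would have been enough.

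**The two tests compared.** All possible pairs of counts at 107 per arm were enumerated with binomial weights. The CMH column here is the uncorrected single-table version; the planning test is shown for reference.

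| True rates (DR vs R) | CMH-type | Fisher | Continuity-corrected chi-squared | CMH-type significant, Fisher not |
|---|---|---|---|---|
| 40% vs 20% | 89.9% | 87.1% | 86.7% | 2.8% |
| 35% vs 20% | 69.9% | 64.4% | 63.8% | 5.5% |
| 33% vs 20% | 58.4% | 52.3% | 51.7% | 6.2% |
| 20% vs 20% (null) | 5.0% | 3.3% | 3.3% | 1.7% |

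Fisher was never significant when the CMH-type test was not.

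**With two strata.** Simulation (400,000 replicates) of stratified CMH against pooled Fisher gave 89.8% to 89.9% against 87.1% to 87.2% at 40% vs 20%, with 2.7% discordant, across the three high-risk shares. With a chance imbalance of 24 against 18 high-risk patients and a prognostic stratum (DR 22% and 36%, R 12% and 22% in high and standard risk), discordance reached 10.5%. Fisher significant with CMH not occurred in less than 0.01% of replicates in every scenario.

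**Worked example** (assumed 21 high-risk and 86 standard/unknown per arm): DR 6/21 + 28/86 = 34/107; R 3/21 + 18/86 = 21/107. In each stratum, the expected DR count under the null is half the stratum's converters, because the arms are equal in size.

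- High risk: observed 6, expected 4.5, variance 1.811
- Standard/unknown: observed 28, expected 23, variance 8.474
- CMH chi-squared = (1.5 + 5)² / (1.811 + 8.474) = 42.25 / 10.285 = 4.11, p = 0.043
- With continuity correction: (6.5 − 0.5)² / 10.285 = 3.50, p = 0.061
- Mantel-Haenszel odds ratio = (6×18/42 + 28×68/172) / (15×3/42 + 58×18/172) = 13.64 / 7.14 = 1.91, 95% CI 1.02 to 3.58
- Fisher on 34/107 vs 21/107: p = 0.060

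The interval excludes 1 and the printed p-value exceeds 0.05. The plan has no rule for whether PFS is then tested.

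**The case against.** The strongest reply is that the intention is clear. The protocol names CMH alone, the SAP names it first, and the subgroup bullet in SAP 5.2.3 describes dropping the stratification factor from the CMH test, which treats CMH as the primary analysis. On this reading the Fisher sentence is a stray line. That supports restoring CMH, but the sentence remains the SAP's only statement of where the p-value comes from.

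Several qualifications stand:

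- Fisher loses nothing against the planning benchmark. The trial was sized on the continuity-corrected test, and Fisher's 87.1% is slightly above that test's 86.7%. The loss of about 3 points is relative to uncorrected CMH.
- The numerical gap comes mostly from the continuity correction rather than from stratification. Corrected CMH in the example gives p = 0.061, close to Fisher, and neither document says whether CMH is corrected. This is a reason to state the setting.
- That Fisher's test would be unstratified is inferred from its standard form. That the SAP's odds ratio is the Mantel-Haenszel one is taken from the protocol.
- The endpoints inheriting the method through SAP 5.4.2 are exploratory under SAP 5.1.1, so no confirmatory decision depends on them.

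**Conclusion.** The concern holds. The SAP contradicts itself and the protocol on the source of the primary p-value, and nothing in either document resolves it. If uncorrected CMH is the reference, the two readings give different decisions in about 3% of trials at the design effect and about 6% when the true difference is near 13 points. Stratum imbalance with a prognostic stratum can raise this to about 10%. Disagreement is almost always in one direction, with Fisher failing where CMH succeeds.

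This is neither a sample-size error nor an alpha problem. Power of at least 85% is met under either test, and size at a 20% null rate is about 5.0% for CMH and 3.3% for Fisher when either is fixed in advance. The stratified figures rest on the assumed high-risk share, and changed little between 15% and 30%. Because the affected test decides the primary endpoint and the gate to PFS, it must be corrected before the analysis.

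**What to change.** In SAP 5.2.3, replace the Fisher sentence with: The two-sided p-value for the primary endpoint is from the stratified CMH test without continuity correction, stratified by cytogenetic risk as used for randomisation; this p-value alone determines whether PFS is tested under Section 5.1.1.

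The uncorrected form is proposed because it is standard and held its size at about 5%. If the sponsor prefers the corrected form, the sentence should say so; what matters is that one version is named. Fisher's exact test may stay as a labelled unstratified sensitivity analysis. The endpoints that refer to 5.2.3 through 5.4.2 then follow the same rule.

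The cost is one sentence in the SAP. No new data and no change to the sample size or the protocol are needed.

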5.4.1. Definition

MRD by NGS are evaluated post-baseline at the end of 12, 18, 24, and 36 months after the start of study treatment(s). The overall MRD negativity (10^{-5}) conversion rate at any time after randomization is defined as the rate of MRD converted from positive at baseline to negativity at the threshold 10^{-5} achieved at any time after randomization.

In addition, MRD negativity (10^{-5}) conversion rate at 12, 18, 24 and 36-months landmark time with +/- 2 months window, as well as accumulative rate up to these timepoints will be summarized. MRD negativity (10^{-5}) CR conversion rates for FAS patients, and MRD negativity (10^{-5}) conversion rates for those achieved CR or better response per computerized algorithm will be summarized in a similar manner.

Durable MRD (≥ 1 year) negativity rate, defined as the proportion of subjects who have achieved MRD negative status (at 10⁻⁵) in 2 bone marrow aspirate examinations that are a minimum of 1 year apart, without any examination showing MRD positive status in between assessments. Subjects who have achieved MRD negative status on or after PD or switch to subsequent antimyeloma therapy before PD, will not be considered MRD negative. Subjects with missing or unevaluable MRD status will be considered as MRD positive.

Similar analysis will be performed for durable MRD (≥6 months) negativity rate.

OS, measured from the date of randomization to the date of the subject's death due to any cause. Subjects who died after consent withdrawal will be considered as having an OS event. Subjects who are lost to follow-up will be censored at the time of lost to follow-up. If the patient is alive and vital status is unknown, then the patient's data will be censored at the date the patient was last known to be alive determined by the maximum collection/assessment date from among selected data domains within the clinical database.

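### The supplemental arm comparison of 12-month MRD conversion among patients who ever reach CR (SAP 5.2.3) is not a randomised comparison and should be shown descriptively

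*SAP*

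**What the plan says.** For the primary endpoint, SAP 5.2.1 states: "The primary endpoint will be analyzed based on FAS". SAP 5.2.3 then gives the method. Each arm's rate gets an exact interval. The stratified CMH "method will be used to test if the MRD conversion rate is the same between the two treatment groups", with an odds ratio, its 95% interval and a p-value from Fisher's exact test.

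The same section continues: "The following supplemental analyses may be performed in a similar manner as described above". The second item on that list is the 12-month conversion rate "for subjects in FAS who achieved CR or better response per computerized algorithm at any time during the study". The third item is the rate of MRD-negative CR conversion by 12 months, with the whole FAS as denominator.

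SAP 5.4.1 returns to the CR subset for landmark and cumulative rates, which "for those achieved CR or better response per computerized algorithm will be summarized in a similar manner". It also defines CR as counted during or after study treatment, up to the first subsequent therapy, and it provides for patients who were in CR or sCR before randomisation. Rates of CR and sCR are themselves secondary endpoints compared between arms (Protocol 11.3.2.1, SAP 5.4.2).

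**The concern.** Randomisation makes the two arms comparable at baseline. It does not make comparable the patients in each arm who later reach CR. If daratumumab brings additional patients into CR, the DR subset contains a kind of patient that the R subset lacks. If those patients convert to MRD negativity at a different rate, the subset shows a difference even where treatment does nothing to MRD.

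The time frame adds to this. A CR first documented after month 12 can decide who enters a 12-month analysis, and membership can change with each later data cut. The SAP attaches no caveat or adjustment to this analysis. An odds ratio and p-value printed beside the primary result would be read as having the same standing.

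**Working it through.** **Inputs from the documents.** SAP 1.4 assumes "40% daratumumab plus lenalidomide versus 20% lenalidomide alone" and "a sample size of 214 patients (ie, 107 patients per treatment group at 1:1 randomization"), tested "at a 2-sided alpha of 0.05 using continuity corrected chi-squared test". No CR rate, and no share of patients in CR at randomisation, is given. Both must be assumed.

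**The plan's own figure.** With n = 107 per arm and pooled rate 0.30, the null standard error is √(0.30 × 0.70 × 2/107) = 0.0627 and the alternative one is √((0.16 + 0.24)/107) = 0.0611. Continuity-corrected power is Φ[(0.20 − 1/107 − 1.96 × 0.0627)/0.0611] = Φ(1.11) = 86.6%. This agrees with the stated minimum of 85%.

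**Model with no treatment effect on MRD.** Let a and d be the CR rates on R and DR. Split patients into those who reach CR on either arm (share a), on DR only (d − a), and never (1 − d). Let their conversion rates be mA, mG and mN, the same in both arms, with

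a·mA + (d − a)·mG + (1 − d)·mN = 0.20.

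Among CR patients, R converts at mA and DR at [a·mA + (d − a)·mG]/d.

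- *All converters in CR on either arm (mG = mN = 0), CR 50/70:* mA = 0.20/0.50 = 40.0%; DR = 0.20/0.70 = 28.6%; OR = (0.286/0.714)/(0.40/0.60) = 0.60.
- *Same, CR 50/60:* DR = 0.20/0.60 = 33.3%; OR = 0.75.
- *Milder (mG = 0.10, mN = 0.02), CR 50/70:* mA = (0.20 − 0.020 − 0.006)/0.50 = 34.8%; DR = (0.174 + 0.020)/0.70 = 27.7%; OR = 0.72.
- *Milder, CR 50/60:* mA = (0.20 − 0.010 − 0.008)/0.50 = 36.4%; DR = (0.182 + 0.010)/0.60 = 32.0%; OR = 0.82.

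The rejection rates below come from simulated trials of 107 per arm, with an unstratified two-sided Fisher test at 0.05.

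| CR, R/DR | Model | Subset OR | False rejection |
|---|---|---|---|
| 50/70 | all converters in CR | 0.60 | about 24% |
| 50/70 | milder | 0.72 | about 12% |
| 50/60 | all converters in CR | 0.75 | about 10% |
| 50/60 | milder | 0.82 | about 6% |

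**Direction.** If the DR-only CR patients convert often (mG = 0.40, mN = 0.02, CR 50/70), then mA = (0.20 − 0.080 − 0.006)/0.50 = 22.8%, DR = (0.114 + 0.080)/0.70 = 27.7% and OR = 1.30. Rejection is about 9% with an uncorrected chi-squared test.

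**When there is no bias.** If the same patients reach CR on both arms, or if CR and MRD conversion are unrelated, the OR is 1.00. Rejection is then about 5% with the uncorrected chi-squared test.

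**Under the planned effect (20% against 40%), all converters in CR.** The FAS odds ratio is (0.40/0.60)/(0.20/0.80) = 2.67. With CR 50/70 the subset rates are 0.20/0.50 = 40.0% and 0.40/0.70 = 57.1%, so OR = (0.571/0.429)/(0.40/0.60) = 2.0. With CR 50/50 the subset OR would be 6.0, and with 40/70 it would be 1.33. The subset result thus depends on the CR rates while the FAS effect stays the same.

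**The case against.** The strongest reply is that nothing is decided by this table. It is optional, the primary test uses the FAS, and SAP 5.1.1 gives alpha only to the primary endpoint and then to PFS. The full-FAS counterpart is already planned. All of this stands and limits the weight of the point.

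It is also fair that membership is not wholly a treatment outcome. For patients already in CR at randomisation it is fixed at baseline, and the bias shrinks as their share grows. That share is not given.

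Three stronger readings are tempting, and the documents do not support them:

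- A reader might infer that SAP 5.4.1 also tests the CR subset. It says only that these rates are summarised, and SAP 5.4.2 does not name them among the endpoints that receive the primary method. There is no odds ratio or p-value there to remove.
- A reader might infer that false findings would occur in nearly half of trials. That needs 30% conversion in both arms, every converter in CR, and CR 50/70 (OR 0.50, rejection about 44% to 46% with Fisher's test). The SAP's control rate is 20%, and the other conditions are near the worst case.
- A reader might infer that the analysis favours DR or contradicts the primary result. Most of the modelled scenarios run against DR, and with the planned effect and CR 50/70 the subset odds ratio still favours DR.

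**Conclusion.** The point holds for the one item in SAP 5.2.3. Comparing arms among patients who reach CR at any time conditions on something treatment may change, so its odds ratio and p-value cannot be read as a treatment effect on MRD. This structural flaw does not depend on any assumed rate.

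Its size does. Bias requires that treatment changes who reaches CR and that CR is associated with MRD conversion. Both are plausible, but the documents quantify neither. At 20% conversion in both arms, the illustrations range from close to the nominal 5% (CR 50/60, milder model) to about 24% (CR 50/70, all converters in CR). The simulations are unstratified and take no account of patients whose CR predates randomisation. The direction cannot be known in advance. The primary FAS analysis and the error control for PFS are unaffected, so this is a modest correction to a supplemental table.

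**What to change.** In SAP 5.2.3, drop the odds ratio, confidence interval and p-value for the CR-ever subset. Show the percentage converting in each arm, with the subset denominators, and label the table as a non-randomised description. Name the FAS rate of MRD-negative CR conversion, already the next item, as the inferential analysis of MRD and CR together.

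If a comparison specific to CR patients is wanted, define the subgroup by CR status at randomisation and add it to the subgroup table in SAP 2.4, where it is not now listed. The baseline response needed for this appears to be available: SAP 5.4.1 plans shift tables from baseline and starts duration of CR at randomisation for patients already in CR.

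In SAP 5.4.1, add the same non-randomised label to the CR-subset summaries.

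The cost is a few lines of SAP text and one fewer test. No new data are needed, and the sample size and primary analysis do not change.
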